characterize and document the reaction as an AE and AESI. Review of the injection site will continue until the AE is resolved.

Each injection site reaction will be categorized using the intensity grading scheme presented in Table 6: the severity of each resulting AE will also be categorized as described in Section 8.7.2.1 (eg, a moderate intensity injection site reaction may be recorded as a mild AE if considered appropriate according to the Investigator's judgment).

Table 6 Injection Site Reaction Grading Scheme

Injection Site Reaction	Absent (Grade 0)	Mild (Grade 1)	Moderate (Grade 2)	Severe (Grade 3)	Potentially Life- threatening (Grade 4)
Pain	Absent	Does not interfere with activity	Repeated use of non-narcotic pain reliever >24 hours or interferes with activity	Any use of narcotic pain reliever or prevents daily activity	Hospital visit (A&E) or hospitalization
Tenderness	Absent	Mild discomfort to touch	Discomfort with movement	Significant discomfort at rest	Hospital visit (A&E) or hospitalization
Erythema/ redness	0 to ≤2.4 cm ^{50a}	2.5 to 5.0 cm ^a	5.1 to 10.0 cm ^a	>10.0 cm ^a	Necrosis or exfoliative dermatitis
Induration/ swelling	0 to ≤2.4 cm ^a	2.5 to 5.0 cm ^a and does not interfere with activity	5.1 to 10.0 cm ^a or interferes with activity	>10.0 cm ^a or prevents daily activity	Necrosis

Abbreviations: A&E = accident and emergency department.

8.7 Adverse Events

The PI and any designees are responsible for detecting, documenting, and recording events that meet the definition of an AE or SAE and remain responsible for following up AEs that are serious, considered related to the IP or study procedures, or that caused the participant to discontinue the study (see Section 7.0). Care will be taken not to introduce bias when detecting AEs and/or SAEs. Open-ended and non-leading verbal questioning of the participant is the preferred method to inquire about AE occurrences.

The method of recording, evaluating, and assessing causality of AE and SAE and the procedures for completing and transmitting SAE reports are provided in the sections below.

a. Measurements refer to the reaction at the greatest single diameter.

8.7.1 **Definitions**

8.7.1.1 Adverse Events

An AE is any untoward medical occurrence in a participant, temporally associated with the use of an IP, whether or not considered related to the IP. An AE can therefore be any unfavorable and unintended sign (including an abnormal laboratory finding), symptom, or disease (new or exacerbated) temporally associated with the use of the IP.

Events meeting the AE definition include:

- Any abnormal laboratory test results (hematology, coagulation, clinical chemistry, or urinalysis) or other safety assessments (eg, ECG, vital signs measurements, physical examinations, or injection site assessments), including those that worsen from baseline, considered clinically significant in the medical and scientific judgment of the PI (ie, not associated with the participant's health status).
- Exacerbation of a chronic or intermittent pre-existing condition including either an increase in frequency and/or intensity of the condition.
- New conditions detected or diagnosed after signing the ICF although it may have been present before the start of the study.
- Signs, symptoms, or the clinical sequelae of a suspected drug-drug interaction.
- Signs, symptoms, or the clinical sequelae of a suspected overdose of either IP or a concomitant medication. Overdose per se will not be reported as an AE/SAE unless it is an intentional overdose taken with possible suicidal/self-harming intent. Such overdoses should be reported regardless of sequelae.

Events that do NOT meet the definition of an AE include:

- Medical or surgical procedures (eg, endoscopy, appendectomy): the condition that leads to the procedure is the AE.
- Situations in which an untoward medical occurrence did not occur (social and/or convenience admission to a hospital).
- Anticipated day-to-day fluctuations of pre-existing disease(s) or condition(s) present or detected at the start of the study that do not represent a clinically significant exacerbation or worsening.

Adverse events which commence or worsen in severity on or after the time of IP administration will be considered as TEAEs.

8.7.1.2 Serious Adverse Events

If an event is not an AE per definitions above, then it cannot be an SAE even if serious conditions are met.

An SAE is defined as any untoward medical occurrence that:

- Results in death
- Is life-threatening: The term 'life-threatening' in the definition of "serious" refers to an event in which the participant was at risk of death at the time of the event. It does not refer to an event, which hypothetically might have caused death, if it were more severe.
- Requires inpatient hospitalization or prolongation of existing hospitalization: In general, hospitalization signifies that the participant has been detained (usually involving a stay of at least 24 hours) at the hospital or emergency ward for observation and/or treatment that would not have been appropriate in the physician's office or outpatient setting.
 - Complications that occur during hospitalization are AEs. If a complication
 prolongs hospitalization or fulfills any other serious criteria, the event is serious.
 When in doubt as to whether "hospitalization" occurred or was necessary, the AE should be considered serious.
 - o Hospitalization for elective treatment of a pre-existing condition that did not worsen from baseline is not considered an AE.
- Results in persistent disability/incapacity: The term disability means a substantial disruption of a person's ability to conduct normal life functions. This definition is not intended to include experiences of relatively minor medical significance such as uncomplicated headache, nausea, vomiting, diarrhea, influenza, and accidental trauma (eg, sprained ankle) which may interfere with or prevent everyday life functions but do not constitute a substantial disruption.
- Is a congenital anomaly/birth defect: Intrauterine development of an organ or structure that is abnormal in form, structure, or position.
- Is a medically important event or reaction: Medical or scientific judgment should be exercised in deciding whether SAE reporting is appropriate in other situations, such as important medical events that may not be immediately life-threatening or result in death or hospitalization but may jeopardize the participant or may require medical or surgical intervention to prevent 1 of the other outcomes listed above. These events should usually be considered serious. Examples of such events include:
 - Laboratory abnormalities that meet the Common Terminology Criteria for Adverse Events (CTCAE) Grade 4 criteria
 - o Invasive or malignant cancers, intensive treatment in an emergency room or at home for allergic bronchospasm, blood dyscrasias or convulsions that do not result in hospitalization, or development of drug dependency or drug abuse.

8.7.1.3 Recording of Adverse Events Based on Other Safety Assessments

For protocol-specified laboratory parameters, any laboratory abnormality that is new in onset or which has worsened in severity or frequency from the baseline condition and meets one of the following criteria will be recorded on the AE pages of the eCRF if not captured as part of an overarching diagnosis (eg, hemoglobin of 8 g/dL captured as part of anemia):

- Requires therapeutic intervention or additional diagnostic tests.
- Has accompanying clinical symptoms or signs.
- Is judged by the PI as clinically significant.

Additionally, any abnormalities in protocol-specified laboratory parameters that meet the CTCAE Grade \geq 3 criteria are considered to be clinically significant and will be recorded as AEs.

Any clinically significant deterioration in vital signs, ECGs, and physical examinations as compared with baseline should also be recorded as AEs.

8.7.2 Recording of Adverse Events

All AEs/SAEs will be recorded from the time of signing the ICF until the end of the participant's participation in the study.

When an AE/SAE occurs, it is the responsibility of the PI or designee to review all documentation (eg, hospital progress notes, laboratory reports, and diagnostics reports) related to the event. The PI or designee will then record all relevant AE/SAE information in the eCRF, including the following details (each event must be recorded separately):

- A description of the event
- Onset and resolution dates and times
- Seriousness
- Severity (as defined in Section 8.7.2.1)
- Relationship to the IP (as defined in Section 8.7.2.2)
- Action taken (none, treatment given, withdrawn from study, nondrug therapy, other)
- Outcome (Fatal, Not recovered/Not resolved, Recovered/Resolved, Recovered/Resolved with sequelae, Recovering/Resolving, or Unknown)

The PI or designee will attempt to establish a diagnosis of the event based on signs, symptoms, and/or other clinical information. Whenever possible, the diagnosis (not the individual signs/symptoms) will be documented as the AE/SAE.

It is not acceptable for the PI or designee to send photocopies of the participant's medical records in lieu of completion of the AE/SAE eCRF page. However, there may be instances when copies of medical records for certain cases are requested by the Medical Monitor and/or Sponsor. In this case, all participant identifiers, with the exception of the participant number, will be redacted on the copies of the medical records before submission to Medical Monitor and/or Sponsor.

8.7.2.1 Assessment of Severity

Based on their clinical judgment, the PI or designee will make an assessment of severity for each AE and SAE reported during the study and assign it to 1 of the following categories:

- Mild: An AE that is easily tolerated by the participant, causes minimal discomfort, and does not interfere with everyday activities.
- Moderate: An AE that is sufficiently discomforting to interfere with normal everyday activities; intervention may be needed.
- Severe: An AE that prevents normal everyday activities; treatment or other intervention usually needed.

Note: the term "severe" does not necessarily equate to "serious". Severity is a measure of intensity whereas seriousness is defined by the criteria in Section 8.7.1.2. An AE of severe intensity need not necessarily be considered serious. For example, nausea that persists for several hours may be considered severe nausea, but not a SAE. On the other hand, a stroke that results in only a limited degree of disability may be considered a mild stroke but would be a SAE.

When changes in the intensity of an AE occur more frequently than once a day, the maximum intensity for the experience should be recorded. If an AE changes in frequency or intensity over a number of days, a new entry of the event must be made in the eCRF (with distinct onset dates).

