9.4.7 Safety Analyses

9.4.7.1 Adverse Events

All safety analyses will be performed on the Safety Population. Adverse events will be coded using the latest version of MedDRA.

All AE summaries will be restricted to TEAEs only (as defined in Section 8.7.1.1). An overview summary of the frequency and percentage of participants with TEAEs overall and by TEAE category will be presented by treatment group and for all participants. Treatment-emergent AEs will also be grouped by SOC and PT and summarized by treatment group and for all participants.

For the summaries of TEAEs, participants who experience the same TEAE (in terms of the MedDRA SOC and PT) more than once will be only counted once for that event in the number of participants, but all occurrences of the same event will be counted in the number of events.

Separate summaries are provided for TEAEs by maximum severity (mild, moderate, or severe) and related TEAEs. Any TEAEs with a missing or unknown severity will be considered as severe in the summary tables. Related TEAEs are considered as those reported as having a relationship to IP of certain, probable, or possible.

Adverse events of special interest, TEAEs of clinically significant laboratory abnormalities, TEAEs of Grade ≥3 laboratory abnormalities, TEAEs leading to discontinuation from the study, SAEs, and TEAEs leading to death will be summarized and listed separately.

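### Does the TEAE definition drop adverse events that began before dosing and became more frequent afterwards?

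*Combined protocol and SAP*

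**What the plan says.** Recording starts before dosing: "All AEs/SAEs will be recorded from the time of signing the ICF" (Section 8.7.2). That section also asks for a separate record of every event, and the details listed for each record include "Onset and resolution dates and times".

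Section 8.7.2.1 deals with events that change: "If an AE changes in frequency or intensity over a number of days, a new entry of the event must be made". The sentence then states that this entry goes into the eCRF with an onset date of its own. The sentence before it covers faster changes: where intensity varies more than once a day, only the maximum is recorded. The same section notes: "Severity is a measure of intensity whereas seriousness is defined by the criteria in Section 8.7.1.2".

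Section 8.7.1.1 defines treatment emergence: "Adverse events which commence or worsen in severity on or after the time of IP administration will be considered as TEAEs". It also lists among the events that are AEs: "Exacerbation of a chronic or intermittent pre-existing condition including either an increase in frequency and/or intensity of the condition". For laboratory parameters, Section 8.7.1.3 covers "any laboratory abnormality that is new in onset or which has worsened in severity or frequency from the baseline condition", provided one of its further criteria is met.

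Section 9.4.7.1 sets the scope of the tables: "All AE summaries will be restricted to TEAEs only (as defined in Section 8.7.1.1"). Within those tables a participant counts once per SOC and PT, while each occurrence adds to the number of events. Section 9.4 leaves detailed procedures to the SAP; its derivation rules are not in the text reviewed.

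**The concern.** Three places treat a rise in frequency as a reportable change: the exacerbation item in Section 8.7.1.1, the laboratory rule in Section 8.7.1.3 and the new-entry rule in Section 8.7.2.1. The worsening part of the TEAE definition names severity alone. Frequency cannot be read into severity, because Section 8.7.2.1 equates severity with intensity and names frequency beside intensity as a separate kind of change.

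Consider a mild complaint that first appears between consent and dosing, occurs weekly, and becomes daily after dosing while staying mild. If the post-dose entry is regarded as a continuation of the same AE, nothing commenced after dosing and severity did not worsen. The event would then be absent from the TEAE overview and from the SOC/PT, related-TEAE and maximum-severity tables, and would appear only in listings. The same post-dose course in a condition known before consent would count, as an exacerbation.

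With 112 participants per group and 336 in total (Section 9.2), each omitted participant would lower a group's TEAE percentage by 1/112 = 0.89 points and the overall percentage by 1/336 = 0.30 points. The PK similarity conclusions would not be touched.

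**Working it through.** The plan gives no figure to reproduce. The check follows the mild complaint through the rules in order.

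1. **Before dosing.** The complaint is recorded because collection starts at consent (Section 8.7.2). Its onset precedes dosing, so this entry is not a TEAE, as intended.
2. **Rise in frequency after dosing.** Section 8.7.2.1 requires a new entry, dated from its own onset. That onset falls after dosing. Section 8.7.2 asks for times as well as dates, so the order can be established even on Day 1.
3. **TEAE definition.** Section 8.7.1.1 joins commencing and worsening in severity with *or*. An entry whose onset is after dosing meets the first condition, and no change in severity is needed.
4. **Summaries.** Section 9.4.7.1 takes in all TEAEs, so the entry is summarised.

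The two possible readings can be compared on five courses, all with onset between consent and dosing:

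| State before dosing, then after dosing | TEAE if each entry is judged by its own onset | TEAE if the entry is treated as a continuation |
|---|---|---|
| Mild, then moderate | yes | yes |
| Mild weekly, then mild daily | yes | no |
| Moderate, then mild | yes | no |
| Mild daily, then mild weekly | yes | no |
| Mild, unchanged | no (no new entry) | no |

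The omission appears only in the right-hand column, second row. That column requires the onset date recorded for the new entry to be set aside in favour of the date of the earlier entry. Nothing in the text reviewed tells the analyst to do that.

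The comparison with a condition known before consent does not show an inconsistency either. The exacerbation item in Section 8.7.1.1 speaks of a pre-existing condition without fixing consent as the reference point, and the general AE definition there is framed around use of the product. A complaint that already recurs before dosing can reasonably be regarded as an intermittent pre-existing condition. Its increase after dosing is then an AE in its own right that commences after dosing, so both cases receive the same answer.

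**The case for a change.** The strongest argument is that Section 8.7.2.1 speaks of a new entry of *the* event, which suggests one continuing AE, and that no sentence equates an entry's onset with commencement of the AE. If every multi-day change starts a new AE, the worsening-in-severity route looks superfluous, so the authors may have meant continuing AEs to be tested for worsening.

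The point about redundancy does not stand. The new-entry rule applies to changes over several days, and intensity that varies more than once a day is recorded at its maximum. An AE that begins on Day 1 before dosing and intensifies later that day may have one entry with a pre-dose onset. The severity route is what makes that event a TEAE, so the two routes do different work.

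What stands is narrower. The text reviewed does not say how linked entries are to be programmed. Judging each entry by its own onset could count an improving AE as treatment-emergent (third and fourth rows of the table). The details listed in Section 8.7.2 include no frequency item, so the direction of a frequency change may not be recoverable from them. This would add events, where the concern is that events are lost. A SAP line stating how such entries are classified would settle it, and a line using each entry's own onset would apply Section 8.7.1.1 as written.

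**Conclusion.** The concern does not hold. An AE that becomes more frequent after dosing receives an entry with a post-dose onset, meets the commencement route of the TEAE definition and enters the summaries. The number omitted under the stated rules is zero, so the 0.89 points per participant in a group does not arise.

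This rests on two assumptions: sites make the entry that Section 8.7.2.1 requires, and the analysis uses the onset date recorded for that entry. If entries were instead linked back to their pre-dose onset, some events could be missed. The documents do not give the number of such events, and any estimate would rest on assumed rates.

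The remaining uncertainty, chiefly the possible over-counting of improving AEs, is a detail for the SAP. The same rule applies in all three groups, and the AE tables are descriptive.

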8.7.2.2 Assessment of Causality

The PI or designee is obligated to assess the relationship between the IP and the occurrence of each AE/SAE. The PI or designee will use clinical judgment to determine the relationship. Alternative causes, such as natural history of the underlying diseases, concomitant therapy, other risk factors, and the temporal relationship of the event to the IP will be considered and investigated. The PI or designee will also consult the IB and/or Product Information for Simponi, in their assessment.

The causal relationship of the AE to the IP or study procedures should be assessed by the PI (or medically qualified delegate) using the following definitions:

Related - there is reasonable possibility that the adverse event has been caused by the IP, meaning there are facts, evidence, or arguments to support the causal relationship, such as:

- plausible time relationship
- supporting de-challenge and/or re-challenge information is available
- participants underlying condition(s), concomitant therapy, disease progression, or other causes or risk factors cannot explain the adverse event

Not-related - there is no reasonable possibility that the adverse event was caused by the IP, meaning there is no evidence suggesting a causal relationship and the adverse event can readily be explained by alternative causes, such as:

- participants underlying condition(s), concomitant therapy, disease progression, or other causes or risk factors
- time relationship does not support causal relationship
- the available de-challenge and/or re-challenge information does not support causal relationship

8.7.3 Reporting of Serious Adverse Events

As the Sponsor has a legal responsibility to notify the appropriate regulatory authorities about the safety of a new test drug, prompt notification by the PI or designee of any SAEs to the Sponsor is required.

All SAEs, whether related or unrelated, will be recorded on a paper SAE Form and submitted to the Sponsor and/or designee within 24 hours of site awareness. The PI or designee will submit any clinically or medically significant updated SAE data to the Sponsor and/or designee within 24 hours of it being available. The procedures for completing and transmitting SAE reports and contact information for SAE reporting can be found in the SAE Form.

Copies of all correspondence relating to reporting of any SAEs should be maintained in the site's study files and will be checked routinely by the study monitor.

8.7.4 Follow-up of AEs and SAEs

After the initial AE/SAE report, the PI or designee is required to proactively follow each participant at subsequent visits/contacts. All AEs/SAEs and AESIs (as defined in Section 8.7.7) documented at a previous visit/contact that are designated as ongoing will be followed up until resolution, stabilization, the event is otherwise explained, or until the participant is lost to follow-up (as defined in Section 7.3). This activity will continue up to Day 75 (11 weeks after IP administration). The PI or designee will ensure that follow-up includes any supplemental investigations as medically indicated or requested by the Medical Monitor and/or Sponsor to elucidate the nature and/or causality of the AE or SAE as fully as possible. This may include additional laboratory tests or investigations, histopathological examinations, or consultation with other health care professionals. For AEs or SAEs that are reported before or on Day 75, follow-up of ongoing events that are considered related to the IP will continue only up to the time of database lock.

The PI or designee is not obligated to actively seek new AEs or SAEs after conclusion of the study participation. However, if the PI or designee learns of any SAE, including a death, at any time after a participant has been discharged from the study, and he/she considers the event

to be reasonably related to the IP or study participation, the PI or designee must promptly notify the Sponsor.

8.7.5 Regulatory Reporting Requirements for Serious Adverse Events

The Sponsor has a legal responsibility to notify both the local regulatory authority and other regulatory agencies about the safety of the IP. The Sponsor will comply with any country-specific regulatory requirements relating to safety reporting to the regulatory authority, national clinical trial pharmacovigilance database (if applicable), IRB/IEC, and PIs.

If the Sponsor considers that an SAE is a SUSAR, it will be reported to the appropriate regulatory authorities by the Sponsor (or designee) within the predefined expedited timelines and according to country-specific regulatory requirements. Investigator safety reports must be prepared for SUSARs according to local regulatory requirements and Sponsor policy and forwarded to PI as necessary. A PI or designee who receives an Investigator safety report describing an SAE or other specific safety information (eg, summary or listing of SAEs) from the Sponsor will review and then file it along with the IB.

If required, individual or expedited reports of SAEs or SUSARs will be submitted by the Sponsor or designee to the IRB/IEC, if appropriate according to local requirements.

